15 STATISTICAL EVALUATION

15.1 Sample Size and Power

The sample size calculation is based on ADAS-Cog v14 rather than ADCOMs as prior information on the treatment effect to be anticipated in the ADCOMs scale is very limited. The sample size at a one-sided type I error rate of 5% and a power of 80% for detecting a difference of 2 points in the change from Baseline between the treatment groups is 78 subjects per arm, if the standard deviation of the change from Baseline is 5 points. It is planned to include ADAS-Cog v14 into the confirmatory testing stream by the use of a hierarchical testing procedure, such that no adjustment of the type I error rate is necessary.

As a drop-out rate of approximately 10% is assumed, the number of subjects randomised should be increased to approximately 174 (87 per treatment group).

Regarding NFM, the sample size of 156 subjects (approximately 78 subjects per treatment group) is sufficient to ensure that any untoward effects with a true proportion of at least 3% are observed in at least one subject within a treatment group with a probability of approximately 90%. An untoward effect with a true proportion of 5% or higher will be detected with a probability of > 98% in a sample of 78 subjects.

The study is planned to enrol 7 to 10 subjects at each study site.

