4.0 ENDPOINTS AND VARIABLES

The primary as well as secondary and other endpoints and its variables are given below.

Primary Efficacy Endpoints

The primary efficacy endpoints of this study are:

- Change from Baseline (Week 0) to Week 12/EOT in the ADCOMs (a composite data derived from Alzheimer's Disease Assessment Scales - Cognitive subscale version 14 [ADAS-Cog v14], Clinical Dementia Rating Scale-Sum of Boxes [CDR-SOB], and Mini-Mental Status Examination [MMSE])
- Change from Baseline (Week 0) to Week 12/EOT in the ADAS-Cog v14 score

Primary Efficacy Endpoints variables

The following primary efficacy variables will be evaluated:

- ADCOMs: a composite score based on ADAS-Cog v14, CDR-SOB and MMSE.
- ADAS-Cog v14

Secondary Efficacy Endpoints

The secondary efficacy endpoints of this study are:

- Change from Baseline (Week 0) to Week 12/EOT of RAVLT score
- Change from Baseline (Week 0) to Week 12/EOT of CDR-SOB score
- Change from Baseline (Week 0) to Week 12/EOT of MMSE score
- Change from Baseline (Week 0) to Week 12/EOT of NPI score
- Change from Baseline (Week 0) to Week 12/EOT of NTB – Executive Domain score (COWAT and CFT)

Secondary Efficacy Endpoints variables

The following secondary efficacy variables will be evaluated:

- RAVLT
- CDR-SOB
- MMSE
- NPI
- NTB – Executive Domain (COWAT and CFT)

ADCOMs-related assessments (ADAS-Cog v14, CDR-SOB and MMSE), RAVLT, NPI and NTB - Executive Domain will be performed at the Baseline (Week 0) and the EOT (Week 12) visits to minimise burden for rater and subject.

MMSE and CDR-SOB will also be performed at Screening.

Safety Endpoints

The safety endpoints of this study are:

- Change in clinical safety laboratory values from Baseline (Week 0) to EOT (Week 12)
- Incidence of adverse events (AEs)
- Change in electrocardiogram (ECG)
- Change in Nerve Function monitoring (NFM) (including NTSS-6, TCNS and neurography (nerve conduction velocity and amplitude) of peripheral sensory and motor nerves)
- Change in Columbia suicide severity rating scale (CSSRS) and the incidence of CSSRS related event
- Abnormality in physical examination
- Change in vital signs

Safety Endpoint variables

The following safety variables will be evaluated:

- Clinical safety laboratory values for haematology, biochemistry and urinalysis
- AEs, serious adverse events (SAEs), and adverse events of special interest (AESIs)
- ECG
- NFM
- CSSRS
- Physical examination
- Vital signs

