7.7.1.1 ADCOMs/ADAS-Cog v14 score

ADCOMs, composite score (0 - 1.97) is derived from ADAS-Cog v14, CDR-SOB, and MMSE. ADAS-Cog v14 score is sum of all 14 items of ADAS-Cog v14. Scoring details for ADCOMs and ADAS-Cog v 14 score are given in Appendix 3.

For analysis of the primary efficacy variables, analysis of covariance (ANCOVA) model will be used to assess the change in ADCOMs/ADAS-Cog v14 score from Baseline (Week 0) to Week 12/EOT. The ANCOVA model will include treatment group as fixed effects and the Baseline value as a covariate.

The primary efficacy hypothesis is:

$$H_0: \mu_P \leq \mu_X$$

$$H_1: \mu_P > \mu_X,$$

where μ_P and μ_X denote the change from Baseline (Week 0) to Week 12/EOT in ADCOMs and ADAS-Cog v14 for the placebo and Xanamem™ treatment groups, respectively. Both tests will be performed at a type I error rate of 0.05 one-sided, with a priori hierarchical handling of multiplicity, based on the least squares means (LS means) for Week 12/EOT. LS means from the ANCOVA will be used to derive 90% and 95% confidence intervals. The primary efficacy analysis will not replace missing Week 12/EOT.

Unless otherwise specified, the ANCOVA will have the following characteristics:

- All subjects in the FAS will be included in the primary efficacy analysis as long as there are both Baseline and valid post-Baseline measurements at Week 12/EOT available.
- The response variable will be the change in ADCOMs score from Baseline (Week 0) to Week 12/EOT visit. Only post-Baseline measurements collected on the EOT will be considered response values.
- The following covariate will be used in the models:
 - Baseline ADCOMs score

- Treatment group
- The following SAS statements will be employed:

```
proc mixed data=xxxx ;
    class <treatment group>;
    model < change ADCOMs score> = <baseline ADCOMs score>
    <treatment group> ;
    lsmeans <treatment group>/ diff cl alpha=0.05;
    lsmeans <treatment group>/ diff cl alpha=0.10;
    ods output lsmean=xxx diffs=xxx;
run;
```

Baseline ADCOMs score, as well as observed and change from Baseline values at post-Baseline visits, will be summarized descriptively.

The analysis described above will be repeated for ADAS-Cog v14. Also analysis will be repeated on PP analysis set for supportive evidence.

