7.7.2.2 Clinical Dementia Rating scale - Sum of Boxes (CDR-SOB) Score

CDR-SOB score (0 – 18) is a sum of all six items of CDR-SOB. CDR-SOB score will be analysed for each visit as actual values and change from Baseline. An exploratory ANCOVA will be performed on the change from Baseline (Week 0) to Week 12/EOT for comparison between the treatment groups, including treatment group as fixed effect, and the Baseline value as a covariate. The analysis described for primary efficacy analysis will be used for CDR-SOB data. Scoring details are given in Appendix 3.

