Appendix 3: Scoring Details of Efficacy Variables

Alzheimer's Disease COMposite Score (ADCOMs)

ADCOMs score is composite score derived from ADAS-Cog v14, CDR-SOB, and MMSE.

The resultant composite score, ADCOMS, is a weighted linear combination of the remaining individual scale items in the final fitted PLS model using the corresponding PLS coefficients as weighting factors see the table. The range of ADCOMS is between 0 and 1.97. Items making contributions to ADCOMS include 4 items of the ADAS-cog; two items of the MMSE, and all six items of the CDR-SOB.

Items selected in the Wold's PLS model and their corresponding PLS coefficients ⁷

Scale	Item name	PLS coefficients
ADAS-cog	Delayed word recall	0.008
	Orientation	0.017
	Word recognition	0.004
	Word finding difficulty	0.016
MMSE	Orientation time	0.042
	Drawing	0.038
CDR-SB	Personal care	0.054
	Community affairs	0.109
	Home and hobbies	0.089
	Judgment and problem solving	0.069
	Memory	0.059
	Orientation	0.078

ADAS-cog: Alzheimer's Disease Assessment Scale–cognitive subscale; CDR-SB: Clinical Dementia Rating, sum of boxes; MMSE: Mini-Mental State Exam; PLS: partial least squares.

The ADCOMS score, which is rescaled decline, will be derived based on the coefficients and corresponding items selected from PLS regression in above table:

ADCOMs score

$$\begin{aligned}
 &= 0.008 * \textit{Delayed word recall (ADAS - cog)} + 0.017 \\
 &* \textit{Orientation(ADAS - cog)} + 0.004 * \textit{Word recognition(ADAS - cog)} \\
 &+ 0.016 * \textit{Word finding difficulty(ADAS - cog)} + 0.042 \\
 &* \textit{Orientation time(MMSE)} + 0.038 * \textit{Drawing(MMSE)} + 0.054 \\
 &* \textit{Personal care (CDR - SB)} + 0.109 * \textit{Community affairs(CDR - SB)} \\
 &+ 0.089 * \textit{Home and hobbies(CDR - SB)} + 0.069 \\
 &* \textit{Judgement and problem solving(CDR - SB)} + 0.059 \\
 &* \textit{Memory (CDR - SB)} + 0.078 * \textit{Orientation(CDR - SB)}
 \end{aligned}$$

It is careful to use the reversed score with regard to MMSE (maximum score for each item – MMSE score of each item). It means that for the derivation of ADCOMS score, (5- MMSE score of ‘Orientation time’) will be used for ‘Orientation time’ and (1-MMSE score for ‘Drawing’) will be used for ‘Drawing’.

Rey Auditory Verbal Learning Test (RAVLT)

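### MMSE and CDR-SOB are scored at Screening and again at Week 0, but the ANCOVAs for ADCOMs, CDR-SOB and MMSE each adjust for one baseline value only, which gives up a modest amount of precision

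*SAP*

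**What the plan says.** **Model.** SAP 7.7.1.1 says of the primary analysis: "The ANCOVA model will include treatment group as fixed effects and the Baseline value as a covariate". SAP 7.7.2.2 gives the CDR-SOB model as "including treatment group as fixed effect, and the Baseline value as a covariate", and SAP 7.7.2.3 does the same for MMSE. Protocol 15.2.3.5 and 15.2.3.6 specify the same covariates. None of the four sensitivity analyses in SAP 7.7.1.1 uses Screening scores.

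**Data.** SAP 4.0 adds: "MMSE and CDR-SOB will also be performed at Screening". The schedule (Protocol Table 1) puts both scales at Screening, Week 0 and Week 12, and ADAS-Cog v14 at Week 0 and Week 12 only. ADCOMs takes four ADAS-Cog items, "two items of the MMSE, and all six items of the CDR-SOB" (SAP Appendix 3).

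**Baseline definition.** SAP 5.2 takes the latest Week 0 observation on or before the date of first dose. For MMSE analysed alone it takes the latest of Screening or Week 0. SAP 5.2 and 8.0 bar Screening MMSE from standing in for a missing ADCOMs component. They say nothing about using it as a separate covariate.

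**Week 0 order.** Protocol 9.4.1.2 gives a list to be followed chronologically. Randomisation and dispensing are step 8, and MMSE and CDR-SOB are step 10.

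**The concern.** A single cognitive score carries measurement error. A second pre-treatment score on the same scale normally predicts part of the Week 12 outcome that the first misses, so adjusting for both lowers the residual variance.

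This matters most for ADCOMs. It is the gatekeeper: ADAS-Cog v14 is confirmatory only if ADCOMs succeeds. Yet Protocol 15.1 sizes the trial on ADAS-Cog v14 because prior information on ADCOMs is very limited. The power of the first test is therefore not known, and precision there is worth having. The scores should already exist, since MMSE and CDR Global at Screening decide eligibility. The SAP also uses both pre-treatment visits elsewhere: nerve function status before treatment is the average of Screening and Baseline (SAP 7.8.4).

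**Working it through.** **1. The plan's own figure.** Protocol 15.1 works at one-sided alpha 5% and 80% power, and supposes an SD of 5 points for the change in ADAS-Cog v14. Its result reads: "detecting a difference of 2 points in the change from Baseline between the treatment groups is 78 subjects per arm".

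- n per arm = 2 × [(1.645 + 0.842) × 5 / 2]² = 77.3, so 78. This reproduces.
- "a drop-out rate of approximately 10% is assumed": 78 / 0.9 = 86.7, so 87 per arm and 174 in all. This reproduces.
- These figures concern ADAS-Cog v14. No SD or power is given for ADCOMs, CDR-SOB or MMSE.

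**2. How much of ADCOMs is scored at Screening** (SAP Appendix 3 weights × item maxima):

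- ADAS-Cog items: 0.008×10 + 0.017×8 + 0.004×12 + 0.016×5 = 0.344
- MMSE items: 0.042×5 + 0.038×1 = 0.248
- CDR boxes: 3 × (0.054 + 0.109 + 0.089 + 0.069 + 0.059 + 0.078) = 3 × 0.458 = 1.374
- Total 1.966, matching the stated 1.97.
- Share also scored at Screening: (0.248 + 1.374) / 1.966 = 82.5% of the theoretical range.
- In a mild population the share is lower. If no box exceeded 1, it would be (0.458 + 0.248) / (0.458 + 0.248 + 0.344) = 0.706 / 1.050 = 67%.

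**3. Gain from a second covariate.** Let S, B and Y be the Screening, Week 0 and Week 12 scores. The proportional fall in residual variance is the squared partial correlation of S and Y given B:

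reduction = (r_SY − r_SB·r_BY)² / [(1 − r_SB²)(1 − r_BY²)]

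All correlations below are assumptions.

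| Assumption | Reduction |
|---|---|
| Screening adds nothing beyond Week 0 (r_SY = r_SB·r_BY) | 0% |
| r_BY 0.70, r_SY 0.65, r_SB 0.85: 0.055² / (0.2775 × 0.51) | 2.1% |
| r_BY 0.70, r_SY 0.65, r_SB 0.80: 0.09² / (0.36 × 0.51) | 4.4% |
| r_BY 0.80, r_SY 0.75, r_SB 0.85: 0.07² / (0.2775 × 0.36) | 4.9% |
| r_BY 0.70, r_SY 0.68, r_SB 0.80: 0.12² / (0.36 × 0.51) | 7.8% |
| All equal to 0.5 / 0.7 / 0.8 | 11.1% / 17.0% / 19.8% |

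The last row is an upper end. It requires Screening to predict Week 12 as well as Week 0 does, and two pre-treatment scores taken 1 to 4 weeks apart to agree no better than scores 12 weeks apart.

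A true-score model avoids that. With reliability λ and 12-week stability s, r_SB = λ and r_BY = r_SY = λs. For a full repeat (CDR-SOB or MMSE), λ = 0.9 and s = 0.85 gives 7.4%; λ = 0.8 and s = 0.95 gives 15.2%.

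For ADCOMs only a partial Screening composite exists. Assume its correlations are 0.9 of those of a full repeat. Then λ = 0.9 and s = 0.85 gives 3.3%, and λ = 0.7 and s = 0.95 gives 9.6%. A simulation with reliability 0.6-0.9 and stability 0.85-0.95, with and without eligibility truncation, gave 3-10%.

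Taken with the fading-correlation rows, the working range is 2-10% for ADCOMs and 2-15% for CDR-SOB and MMSE.

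**4. What that is worth.**

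- Extra completers: 156/0.98 − 156 = 3; 156/0.90 − 156 = 17.
- Power, if it were 80% under the planned model: Φ(2.487/√0.98 − 1.645) = 80.7%; Φ(2.487/√0.90 − 1.645) = 83.5%.
- Confidence interval width: 1 − √0.98 = 1.0% narrower; 1 − √0.90 = 5.1% narrower.
- Cost: one degree of freedom, about 1/153 = 0.7% of variance with 156 completers.

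**The case against.** The case for leaving the plan alone has substance.

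- **The planned ANCOVA is valid and consistently pre-specified** in protocol and SAP. That stands. A reader might infer bias; the documents give no ground for it.
- **The gain may be small.** That stands too. No correlations are given, Screening scores are range-restricted by eligibility (MMSE 20 to 26, CDR Global 0.5 to 1.0), and Protocol 9.4.1.1 anticipates learning effects. Restriction shrinks the gain without invalidating the covariate, and a common learning shift goes into the intercept.
- **Larger figures are tempting.** A 15% reduction, or about 27 completers, applies at best to CDR-SOB and MMSE, which are exploratory. The 82.5% is a share of range and cannot be read as a share of information or variance.
- **MMSE is not tied strictly to Week 0.** SAP 5.2 lets Screening substitute, so for such subjects one number would enter twice unless a rule prevents it.
- **More than one program line changes.** The imputation models, SAP 10.0 and comparability with the interim analysis are all touched.

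A further stronger reading is that both scores precede randomisation, or conversely that the Week 0 scores follow randomisation and dosing and are contaminated. Neither is established. Taken literally, the Week 0 list puts the scales after randomisation, but it also describes drug intake at step 3, before dispensing at step 8, so it cannot be literal throughout. SAP 5.2 accepts any score on the date of first dose and does not settle the matter. What can be said is that Screening is the only MMSE and CDR-SOB assessment clearly taken before randomisation.

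**Conclusion.** The point holds as an efficiency matter. Two MMSE and CDR-SOB assessments are scheduled by Week 0, each model uses one, and nothing in the SAP bars the other as a covariate. The omission is certain; the size of the gain is not. A reasonable expectation is 2-10% less residual variance for ADCOMs and 2-15% for CDR-SOB and MMSE, before the 0.7% cost, and nothing if Screening carries no information beyond Week 0. Under the least favourable assumptions the net benefit is close to nil; elsewhere it is modest and nearly free. ADAS-Cog v14, on which the sample size rests, gains nothing from a repeat of its own because none is taken. Label: cheap improvement.

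**What to change.** Before unblinding:

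- In SAP 7.7.1.1 (ADCOMs only), 7.7.2.2 and 7.7.2.3, add the Screening score as a second covariate. Use Screening CDR-SOB for CDR-SOB and Screening MMSE for MMSE. For ADCOMs use the Appendix 3-weighted sum of the six Screening CDR boxes and the two reversed Screening MMSE items, or the two Screening totals if item scores were not entered. Leave the definitions of Baseline and of change as they are, and leave the ADAS-Cog v14 model unchanged.
- Put the same covariate in both multiple-imputation models, so that imputation and analysis models agree. Keep it in the resampling dataset, whose KEEP list would otherwise drop it.
- State which Screening value is used for re-screened subjects, since Protocol 9.4.1.1 lets some of them repeat only selected assessments.
- Give a rule for missing Screening values, and one for MMSE subjects whose Screening value already serves as Baseline. The argument in sensitivity analysis 4 that only Week 12 can be missing depends on the first rule.
- Record the change in SAP 10.0, which now reads as not applicable.
- Separately, reconcile the Week 0 order in Protocol 9.4.1.2 with the baseline definition in SAP 5.2.

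The cost is SAP wording, minor reprogramming, one degree of freedom per model, and a final model that differs from the one used at the interim analysis. If the sponsor prefers not to alter the primary model, the same analysis can be pre-specified as a sensitivity analysis. No new data are needed.

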Whilst the European Medicines Agency discussion paper⁵ foresees the use of the linear models for sensitivity analyses, complementing different methods of primary analyses, the type and order of analyses in this study – ANCOVA as primary efficacy analysis and placebo-based imputation as sensitivity analysis – are chosen in a different fashion due to the following reasons:

- The development stage this study is associated with, where the primary aim is to explore a possible therapeutic effect of Xanamem™; in conjunction with
- The relatively short study duration, which can be expected to reduce the number of missing values in either treatment group and
- The fact that the primary efficacy variables will only be assessed at Baseline (Week 0) and Week 12/EOT.

Sensitivity analyses aim at assessing the robustness of the primary efficacy analysis. The following four analyses will be performed:

1) An additional ANCOVA, imputing missing Week 12/EOT data based on resampling from the placebo subjects, taking Baseline values into account

Process

- a) Select records from placebo group with non-missing ADCOMs score at Week 12
- b) Select records from Xanamem group with missing ADCOMs score at Week 12

- c) Merge datasets from a) and b)
(Total number of records in merged dataset = number of records in dataset a) * number of records in dataset b))
- d) Using Baseline (placebo) and Baseline (Xanamem), calculate DIFF variable to find record in placebo group which has smallest in difference with Baseline in test group
DIFF = abs (Baseline (Xanamem) – Baseline (placebo))
- e) Calculate RANDNO variable with RANUNI function and select the smallest randno
- f) Select 1 record for each missing case in Xanamem group and impute ADCOMs score at Week 12 based on ADCOMs score at Week 12 in placebo group
- g) Calculate change from Baseline based on imputed ADCOMs score at Week 12 for Xanamem group
- h) Repeat a) to g) for placebo group and combine both datasets with the records from both groups with non-missing ADCOMs score at Week 12.
- i) Run proc ANCOVA specified above

The following SAS statements will be employed:

For Xanamem group:

```

data placebo;
set indata;
if <treatment group> = Placebo and <VISIT> = Week 12 and AVAL <> missing;
rename CHG=CHG_P BASE=BASE_P ID=ID_P AVAL=AVAL_P;
run;

```

```

data test;
set indata;
if <treatment group> = Test and <VISIT> = Week 12 and AVAL = missing;
run;

```

```

proc sql;
create table outdata as
select *from test, placebo ;

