var <baseline ADCOMs score> < ADCOMs score at week 12/EOT>;
run;

data zzzz;
set yyyy;
<change ADCOMs score> = <ADCOMs score at week 12/EOT> -< baseline
ADCOMs score>;
run;

* For 95% Confidence Interval;
proc mixed data=zzzz;
by _imputation_;
class <treatment group>;
model <change ADCOMs score>=<baseline ADCOMs score> <treatment
group>;
lsmeans <treatment group>/ diff cl alpha=0.05;
ods output lsmeans=aaaa diffs=bbbb;
run;

** LSmeans;
proc mianalyze parms(classvar=full)=aaaa;
class <treatment group>;
modeleffects <treatment group>;
ods output parameterestimates=cccc;
run;

** Differences;

```

```

proc mianalyze parms(classvar=full)=bbbb;
class <treatment group>;
modeleffects <treatment group>;
ods output parameterestimates=dddd;
run;

* For 90% Confidence Interval;
proc mixed data=zzzz;
by _imputation_;
class <treatment group>;
model <change ADCOMs score>=<baseline ADCOMs score> <treatment
group>;
lsmeans <treatment group>/ diff cl alpha=0.10;
ods output lsmeans=aaaa2 diffs=bbbb2;
run;

** Differences;
proc mianalyze parms(classvar=full)=bbbb2;
class <treatment group>;
modeleffects <treatment group>;
ods output parameterestimates=dddd2;
run;

```

The analysis described above will be repeated for ADAS-Cog v14.

4) An additional ANCOVA, imputing missing Week 12/EOT data based on multiple imputation using both the Xanamem and placebo group with the missing at random (MAR) assumption.

Process

Missing data at Week 12/EOT will be imputed using a regression based imputation model. The imputation model will include Treatment Group, Baseline values and Week 12/EOT values. The imputation model for the missing observations in both the Xanamem group and the placebo group will be constructed from the complete-case observed data for patients in both the Xanamem group and the placebo group. Under this approach we assume that patients with

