missing data in each treatment group would have outcomes like a complete-case patient in that treatment group, where a complete-case patient is one with no missing values for any of the variables in the imputation model. This is known as the complete-case missing values (CCMV) approach. By study design, all patients will have non-missing data for Baseline and Treatment Group. Therefore Week 12/EOT is the only variable in the imputation model which can possibly have missing values. Since there is only one possible missing data pattern for the ADCOMs analysis, an imputation model based on complete-case patients only (CCMV) is equivalent to an imputation model based on patients with any missing data pattern. For this reason, although CCMV is usually a MNAR approach, for the specific case of the ADCOMs analysis (and ADAS-Cog v14 analysis), it is equivalent to a MAR approach.

The imputation will be performed 100 times and imputed datasets will be analysed using an ANCOVA model. Approximately 100 imputed datasets will be created and results from the analysis of each imputed dataset will be combined using Rubin's method.

- The following SAS statements will be employed:

```
proc mi data=xxxx nimpute=100 seed=3489876 out=yyyy;  
class < treatment group>;  
monotone reg (<ADCOMs score at week 12/EOT>);  
mnr model(<ADCOMs score at week 12/EOT>/modelobs=ccmv);  
var <treatment group> <baseline ADCOMs score> < ADCOMs score at week  
12/EOT>;  
run;  
  
data zzzz;  
set yyyy;  
<change ADCOMs score> = <ADCOMs score at week 12/EOT> – <baseline  
ADCOMs score>;  
run;  
  
* For 95% Confidence Interval;  
proc mixed data=yyyy;  
by _imputation_;  
class <treatment group>;
```

```
model<change ADCOMs score>=<baseline ADCOMs score> <treatment
group>;
lsmeans <treatment group>/ diff cl alpha=0.05;
ods output lsmeans=aaaa diffs=bbbb;
run;
```

```
** LSmeans;
proc mianalyze parms(classvar=full)=aaaa;
class <treatment group>;
modeleffects <treatment group>;
ods output parameterestimates=cccc;
run;
```

```
** Differences;
proc mianalyze parms(classvar=full)=bbbb;
class <treatment group>;
modeleffects <treatment group>;
ods output parameterestimates=dddd;
run;
```

```
* For 90% Confidence Interval;
proc mixed data=yyyy;
by _imputation_ ;
class <treatment group>;
model<change ADCOMs score>=<baseline ADCOMs score> <treatment
group>;
lsmeans <treatment group>/ diff cl alpha=0.1;
ods output lsmeans=aaaa2 diffs=bbbb2;
run;
```

```
** Differences;

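### SAP code for the two multiple-imputation sensitivity analyses repeats the 95% limits under a 90% label, and in analysis 4 fits a dataset that lacks the recomputed change score

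*SAP*

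**What the plan says.** SAP 7.7.1.1 tests both primary endpoints at one-sided 0.05 and plans 90% and 95% intervals from the ANCOVA. The primary code obtains the 90% limits directly with "lsmeans <treatment group>/ diff cl alpha=0.10". No pooling step follows, so the level is set where the limits are computed.

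Sensitivity analyses 3 and 4 impute missing Week 12 scores 100 times, fit the ANCOVA to each imputed dataset and combine the results by Rubin's method. For analysis 4 the prose reads: "The imputation will be performed 100 times and imputed datasets will be analysed using an ANCOVA model". For both analyses the SAP commits to the SAS statements it prints.

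The two listings have the same structure:

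- **Imputation.** "proc mi data=xxxx nimpute=100 seed=3489876 out=yyyy" writes the imputed Week 12 scores to `yyyy`.
- **Change score.** A data step reads `yyyy`, recomputes change as Week 12 minus Baseline, and writes `zzzz`.
- **Model.** Analysis 3 uses "proc mixed data=zzzz" in its 95% and 90% blocks. Analysis 4 uses "proc mixed data=yyyy" in both.
- **Pooling of the treatment difference, 90% block.** Both analyses use "proc mianalyze parms(classvar=full)=bbbb2", with no confidence level given.

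**The concern.** **(a) Interval level, analyses 3 and 4.** The level on LSMEANS affects only the limits of each single-imputation fit. Rubin's method pools estimates and standard errors and discards those limits. The level has to be given at the pooling step, and it is not. The 90% interval matters because it is the two-sided counterpart of the one-sided 0.05 test. A reader comparing the correct primary 90% interval with a wider pooled interval under the same label could blame the missing data for the extra width.

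**(b) Dataset, analysis 4.** The imputed Week 12 values reach the response variable only through `zzzz`, which is never read. If the code runs at all, it re-reports the observed-case result as support from a missing-at-random imputation that has not entered the model.

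**Working it through.** **Design figures (Protocol 15.1).** Difference 2, SD 5, one-sided 5%, power 80%: n = 2 × (1.645 + 0.842)² × 5² / 2² = 77.3, so 78 per arm, as stated. With 10% drop-out, 78 / 0.9 = 86.7, so 87 per arm and 174 in total, also as stated. The illustrations below therefore use 174 randomised, 156 observed and 18 missing.

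**Part (a): tracing the two blocks.**

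| Step | 95% block | 90% block |
|---|---|---|
| LSMEANS level | 0.05 | 0.10 (analysis 3), 0.1 (analysis 4) |
| Estimate and SE passed on | same | same |
| Pooling input | `bbbb` | `bbbb2` |
| Level at pooling | none | none |

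Rubin's total variance is T = W + (1 + 1/m)B, where W is the mean squared SE, B the variance of the estimates and m = 100. The limits are the pooled estimate ± t × √T. Neither W nor B depends on the LSMEANS level, so the two blocks give the same limits whatever the software default is. If that default is 0.05 (an assumption), the critical value is 1.960 instead of 1.645, a ratio of 1.960 / 1.645 = 1.19.

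One simulated dataset shows this (87 per arm, 9 missing per arm, SD of change 5, true difference −2; baseline mean 30 and SD 8 are assumptions):

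| Analysis | Difference (SE) | 90% block as coded | True 90% |
|---|---|---|---|
| 3 | −2.345 (0.751) | −3.818 to −0.872 | −3.581 to −1.109 |
| 4, fitted to `zzzz` | −2.534 (0.740) | −3.985 to −1.083 | −3.752 to −1.316 |

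The as-coded column is also the 95% interval.

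Over 500 simulated trials of a correctly fitted analysis 4 (same sizes; baseline SD 8 and slope −0.1 assumed), the half-width was 1.555 points at 95% and 1.305 at 90%, ratio 1.192. The pooled SE was only 1.002 times the complete-case SE, so almost none of the extra width comes from missing data.

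At the design values the level itself makes a visible difference. SE = 5 × √(2/78) = 0.80 and 2 / 0.80 = 2.50. The chance that the interval excludes zero in favour of the drug is Φ(2.50 − 1.645) ≈ 80% at the 90% level and Φ(2.50 − 1.960) ≈ 70% at the 95% level.

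**Part (b): what `yyyy` contains.** PROC MI imputes the Week 12 score, not the change. There are two cases:

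- *The input already carries a change score.* It stays missing for imputed subjects, PROC MIXED drops them, and all 100 fits are the same. In simulation every fit had n = 156 and B = 0. In the dataset above the result was −2.552 (SE 0.740), exactly the observed-case ANCOVA.
- *The input carries no change score.* The response variable does not exist in `yyyy` and the step fails.

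The first case looks likelier. The primary model, "proc mixed data=xxxx", takes its change score from a dataset with the same placeholder name as the PROC MI input, and the input to analysis 1 carries one too ("rename CHG=CHG_P BASE=BASE_P ID=ID_P AVAL=AVAL_P"). Placeholder names are weak evidence, but neither case gives the planned analysis.

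**Size of (b).** Correct analysis 4 minus complete case, 500 trials: mean −0.002, mean absolute 0.021, maximum 0.078 points. Between-imputation variance is about 10% of the total when coded correctly and 0 as coded.

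**Range.** Over baseline SD 5 to 10, slope 0 to −0.3, and 18 or 34 missing (200 trials each), the half-width ratio was 1.192 throughout. The mean absolute difference was 0.017 to 0.033, the maximum 0.061 to 0.156, and the SE ratio 1.002 to 1.004.

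**The case against.** Neither defect can be disputed from the text, so the strongest objection is that they hardly matter.

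- **Part (b) has almost no numerical effect.** The imputation model holds only treatment, baseline and Week 12, the ANCOVA uses the same terms, and there is no intermediate efficacy visit. A correct missing-at-random imputation therefore reproduces the observed-case result apart from Monte Carlo noise. The figures agree. SE = 1.555 / 1.96 = 0.793, so T = 0.629. A 10.5% share gives B ≈ 0.065, and √(0.065 / 100) × 0.798 ≈ 0.020, against the simulated 0.021. This stands.
- **Part (a) has no decision role.** The confirmatory test is the primary ANCOVA, whose 90% limits are coded correctly. Sensitivity analysis 2 requests only 95% limits, so the SAP does not consistently call for a 90% interval outside the primary analysis. This stands, but analyses 3 and 4 do produce an interval labelled 90%, and the label is wrong.
- **The listings are templates and the errors would show.** Identical limits under two labels, or n = 156 in every fit, might well be noticed. But the SAP gives seeds, options and dataset flow and says the statements will be used. A programmer who corrects them departs from the final SAP.
- **The FAS definition.** Read literally, it limits change-from-baseline analyses to subjects with a post-Baseline value, which would exclude those to be imputed. SAP 8.0 allows imputation for sensitivity analyses of the primary endpoints, so this correction need not touch the FAS wording.

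**Conclusion.** Both errors are real and follow from the printed code.

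- **Analyses 3 and 4:** the pooled 90% and 95% limits are identical, which needs no assumption about software. That the 90% label is the wrong one, by a factor of 1.19 (half-width 1.56 instead of 1.31 ADAS-Cog points under the simulation assumptions), rests on a 0.05 default at the pooling step.
- **Analysis 4:** the missing-at-random analysis described in the prose is not carried out. It becomes a copy of the observed-case ANCOVA or fails, depending on whether the PROC MI input holds a change score.

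The harm is limited. The primary analysis, analysis 1, and the pooled estimates, SEs and 95% limits of analysis 3 are unaffected. The interval error is conservative. A correct analysis 4 would differ from the observed-case estimate by about 0.02 points on average, and by at most 0.16 in the scenarios simulated, against a planned effect of 2. The code should be corrected, but the confirmatory conclusion does not depend on it.

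**What to change.** Make four edits in SAP 7.7.1.1:

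1. Analysis 4, 95% block: change `data=yyyy` to `data=zzzz` in PROC MIXED.
2. Analysis 4, 90% block: make the same change.
3. Analysis 3, 90% block: add `alpha=0.10` to the PROC MIANALYZE call on `bbbb2`.
4. Analysis 4, 90% block: add `alpha=0.10` to the PROC MIANALYZE call on `bbbb2`.

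Carry the edits over to the ADAS-Cog v14 repeats, which the SAP says follow the same code. No new data are needed and the planned analyses do not change.
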